8.3 Adverse Events

Adverse events (AE) will be coded by System Organ Class (SOC) and preferred term using Medical Dictionary for Regulatory Activities (MedDRA), version 18.0. AE severity will be based on National Cancer Institute (NCI) Common Terminology Criteria for Adverse Events (CTCAE) Grade (version 4.03).

A treatment-emergent AE (TEAE) is defined as defined as any event not present prior to the initiation of the treatments or any event already present that worsens in either intensity or frequency following exposure to the treatments. An AE that was present at treatment initiation, but resolved and then reappeared while the patient was on treatment, is a TEAE (regardless of the intensity of the AE when the treatment was initiated). If the start date of an AE is unavailable or incomplete, the AE CRF asks the subject/investigator to identify whether it occurred before the first treatment, during treatment, within 24 hours after the last treatment, or more than 24 hours after the last treatment. This information will be used to determine if the AE will be considered as TEAE, when necessary. If the start time of the AE is provided, then the AE start date and time will be used to classify the AE as TEAE or not. If the start time is not provided and the AE occurs on the same day of first study drug administration (C1D1) then the AE will be classified as TEAE.

Adverse event data will be descriptively evaluated by treatment arm and for overall subjects. Incidence of TEAEs by MedDRA SOC, preferred term, and relationship (Related/Not Related) to study drug will be summarized based on the safety population. Adverse event incidence rates will be summarized with frequency of events, frequency of subjects affected and percentage (based on # subjects affected).

For subject level summaries, subjects with multiple occurrences of events with the same preferred terms and SOC will be counted once at the highest Grade and the strongest relationship to study drug for each preferred term, and system organ class.

Adverse events that are reported as possibly or probably related to study drug will be counted as related to study drug. Adverse events that are reported as unlikely related and unrelated will be summarized as not related. AEs with a missing relationship will be considered “Related” for this summary.

The adverse events summaries listed in [Table 3](#) will be provided for study cohort, integrated treatment group, and totals for the table for the safety analysis set:

Table 3: AE tables produced for treatment with and without stratification

AE Summary	Study Cohort	Integrated Treatment Group

AE Summary	Study Cohort	Integrated Treatment Group
TEAEs summary	Y	Y
TEAEs by System Organ Class and Preferred Term	Y	Y
TEAEs by Preferred Term and by Descending Incidence	Y	N
TEAEs by System Organ Class and Preferred Term and CTCAE Grade	Y	N
Grade 3 or Higher TEAEs by System Organ Class and Preferred Term	Y	N
Serious TEAEs by System Organ Class and Preferred Term	Y	Y
Non-Serious TEAEs by System Organ Class and Preferred Term and by Descending Incidence	Y	N
Serious TEAEs by System Organ Class and Preferred Term and CTCAE Grade	Y	N
Treatment-Related TEAEs by System Organ Class and Preferred Term	Y	N
Treatment-Related TEAEs by Preferred Term and by Descending Incidence	Y	Y
Treatment-Related TEAEs by System Organ Class and Preferred Term and CTCAE Grade	Y	N
TEAEs Leading To Study Drug Discontinuation by System Organ Class and Preferred Term	Y	Y
TEAEs Leading To Study Drug Discontinuation by System Organ Class and Preferred Term and CTCAE Grade	Y	N
TEAEs Leading to Death by System Organ Class and Preferred Term	Y	Y

Listings of all AEs and also all serious AEs will be produced.

A Listing will be produced for AEs with genetic information, actual drug received, and cycles on treatment.

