8.7.4 Description of Treatment

In both Parts 1 and 2, imalumab administration will occur QW, and 5FU/LV or panitumumab administration will occur Q2W in 4-week cycles. Treatment schedule for SoC drugs will be in accordance with the respective product label.

For all subjects in Parts 1 and 2, treatment will continue until disease progression, excessive toxicity, withdrawal of consent, or for any other reason as detailed in Section 9.3.

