13.4.4.2 Safety Outcome Measures

The safety outcome measures are (see Section [8.4.2.2](#)):

- Occurrence of SAEs and/or TEAEs, regardless of causality or relationship to study drug using NCI CTCAE v4.03
- Other safety measurements: physical or instrumental examinations, ECGs, vital signs, clinically relevant changes in instrumental examinations or laboratory values

Adverse events will be regarded as treatment emergent (ie, TEAEs) if they started on or after the date and time of administration of the first dose of study drug, or if they were present prior to the administration of the first dose of study drug and increased in severity during the study.

The number of subjects who experience SAEs and TEAEs will be tabulated and summarized by treatment group. The total number of subjects and events and the corresponding rates will be presented.

In addition, tables will be prepared to list each AE, the number of subjects in each treatment group who experienced an AE at least once, and the rate of subjects with AE(s). Adverse events will be grouped by system organ class. Each event will then be divided into defined severity grades (as described in Section [12.1.2.1](#)). The tables will also divide the AEs into those considered related (a “possibly related” or a “probably related” AE will be considered as a “related AE”) to the treatment and those considered unrelated (an “unlikely related” or an “unrelated” AE will be considered as an “unrelated” AE).

All AEs for each subject, including the same event on several occasions, will be listed, detailing both the MedDRA preferred term and the original verbatim term used by the investigator, system organ class, severity grade, seriousness, relation to the treatment, onset date, and stop date.

Electrocardiograms and vital signs will be summarized using appropriate descriptive statistics. For each clinical laboratory value and change from baseline, summaries will be made via descriptive statistics (ie, mean, median, standard deviation, and range). A summary table showing incidence of clinically significant treatment-emergent laboratory values will be provided. Shift tables showing incidence of new or worsening clinically significant findings from baseline to endpoint will be provided.

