2. STUDY DESIGN

This study is Phase 2a, randomized, open-label study to assess the safety, tolerability, and efficacy of imalumab in combination with 5-FU/LV or panitumumab versus Standard of Care (SOC) in subjects with metastatic colorectal cancer.

This study will be conducted in approximately 40 study sites in the United States (US) and the European Union (EU). The study will comprise 2 sequential parts (subjects can only participate in either Part 1 or Part 2 of the study):

- Part 1: A Safety Run-in period to evaluate 2 predefined doses (7.5 mg/kg and 10 mg/kg) of imalumab given every week (QW) in combination with infusional 5-FU/LV given every 2 weeks (Q2W) in subjects with mutated tumors (KRAS mut, NRAS mut), or imalumab in combination with panitumumab given Q2W in subjects with wild type tumors (KRAS wt and NRAS wt). Prior to entry into the study, subjects will be stratified according to their KRAS/NRAS mutation status. Treatments will be administered in 4-week (28-day) cycles.
- Part 2: A 2-treatment-arm design using a 2:1 ratio for subjects to receive imalumab + 5-FU/LV or imalumab + panitumumab (Arm A) or SoC per investigator choice (Arm B). Prior to randomization, subjects will be stratified according to their mutation status. Within each stratum, subjects will be randomized in a 2:1 ratio to receive imalumab + 5-FU/LV (KRAS mut, NRAS mut tumors) or imalumab + panitumumab (KRAS wt and NRAS wt tumors) (Arm A) or SoC per investigator choice (Arm B).

For all subjects in Parts 1 and 2, treatment will continue until disease progression, unacceptable toxicity, or withdrawal of consent.

Part 1: Safety Run-in

For each combination, subjects will be enrolled into 2 sequential cohorts, with a minimum of 3 and a maximum of 6 subjects per cohort.

For each combination, enrollment will proceed according to the following rules based on the occurrence of dose-limiting toxicities (DLTs):

- If zero out of 3 evaluable subjects experience a DLT during the first 28 days after the first administration of study drug at the first dose level, the second dose level

will be opened for enrollment after review of the safety data by the Data Review Committee (DRC).

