2.3 Sample Size and Power Calculations

The final sample size of Part 1 (Safety Run-in) is dependent on the pre-stated rules for dose escalation. In Part 1, the sample size for each dosing regimen (ie, imalumab + 5-FU/LV and imalumab + panitumumab) is expected to be between 6 and 12 subjects (ie, 3 to 6 subjects at each 7.5 mg/kg and 10 mg/kg imalumab dose level). Non-evaluable subjects will be replaced to meet study objectives.

The sample size of Part 2 (Exploratory Phase 2a) is estimated to be a total of 66 subjects. Assuming that the median PFS is 2.4 months in the control arm and 4.25 months in the experimental arm (a constant hazard ratio 0.565), and using a one-sided log-rank test with α of 0.15 and β of 0.20 with a drop-out rate of 20% at 6 months, 48 PFS events are needed. With an enrollment ratio of 2:1, and taking into account the time for accrual of 1 year and an additional follow-up period of 6 months after the last subject is enrolled, the sample size needed is approximately 22 subjects in each of the 2 imalumab-containing treatment arms (imalumab + panitumumab and imalumab + 5-FU/LV) and in the control arm (SoC).

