8.2 Extent of Exposure

The following variables will be calculated:

- Exposure duration (days): date of last dose – date of first dose (C1D1) + 7, 7 is added to exposure duration to account for the 7-day rest period between imalumab administrations.
- Number of cycles: Total number of complete or partial treatment cycles the subject received.
- Number of Subjects with dose interrupted/ dose reduction

For imalumab, the following parameters will be calculated:

- Cumulative dose (mg): Total actual dose (mg) the subject received across all cycles, defined as the sum of actual dose (mg) received across all cycles.
- Calculated cumulative dose level (mg/kg): Cumulative dose (mg) divided by the average weight (kg) across all cycles.
- Dose intensity (mg/kg/week): {Calculated cumulative dose level (mg/kg) / (exposure duration (days))} x 7
- Expected dose intensity (mg/ kg/week): 7.5 or 10 mg/kg/week based on treatment arm
- Relative dose intensity (%): ((Dose intensity) / (expected dose intensity)) × 100.

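### AE tables by arm give only event counts and crude subject percentages, which would overstate Arm A risk by about 5–9 points for AEs that accrue over time if the planned PFS effect is real

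*SAP*

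**What the plan says.** SAP 8.3 provides that "Adverse event data will be descriptively evaluated by treatment arm and for overall subjects", and that "Adverse event incidence rates will be summarized with frequency of events, frequency of subjects affected and percentage". SAP Table 3 lists 14 AE summaries by study cohort, some also by integrated treatment group. None uses person-time, time to first event or a common observation window. Protocol 13.4.4.2 is no more specific: "The total number of subjects and events and the corresponding rates will be presented", with no time denominator.

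On duration, SAP 2 states: "For all subjects in Parts 1 and 2, treatment will continue until disease progression, unacceptable toxicity, or withdrawal of consent". Protocol 12.1.2 collects TEAEs until study completion or discontinuation, or 30 (±7) days after the last IP treatment. The sizing paragraph in SAP 2.3 reads "Assuming that the median PFS is 2.4 months in the control arm and 4.25 months in the experimental arm", with 20% drop-out at 6 months, 1 year of accrual and 6 months of further follow-up.

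SAP 8.2 defines one exposure duration, last dose minus first dose plus 7 days, because "7 is added to exposure duration to account for the 7-day rest period between imalumab administrations". It stands above the separate list of imalumab-only parameters. For the control arm, Protocol 8.7.4 says "Treatment schedule for SoC drugs will be in accordance with the respective product label". The footnotes to Protocol Tables 4 and 5 allow 3-week or 4-week SoC cycles, and Protocol 8.2.2 allows best supportive care.

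**The concern.** A crude percentage estimates the chance of an AE over however long each subject happened to be observed. When observation ends soon after progression and one arm progresses later, that arm has more time in which to record a first event. Equal underlying toxicity then gives unequal percentages. The distortion appears when the drug works as planned, which is when benefit and risk will be weighed together. These tables are the main between-arm safety evidence in Part 2.

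The exposure variable that would help a reader interpret the percentages has its own defect: its 7 days fit imalumab and no other schedule, and best supportive care may have no last dose.

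**Working it through.** **Planning figures reproduced.** 2.4/4.25 = 0.565, the stated hazard ratio. Schoenfeld's formula with 2:1 allocation, one-sided α 0.15 and power 80% gives (1.036 + 0.842)² / [(2/9)(ln 0.565)²] = 48.7 events, against 48 stated; 48 events give 79.6% power.

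**Time on treatment.** Assume exponential PFS, treatment ending at progression or drop-out, and administrative censoring uniform between 6 and 18 months.

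- PFS hazards: ln2/4.25 = 0.1631 (A) and ln2/2.4 = 0.2888 (B) per month.
- Drop-out hazard: −ln(0.8)/6 = 0.0372 per month.
- Mean time for total exit hazard L: m(L) = (1/L)·[1 − (e^(−6L) − e^(−18L))/(12L)].

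| | Arm A | Arm B | Ratio |
|---|---|---|---|
| Ratio of planned medians (months) | 4.25 | 2.4 | 1.77 |
| Mean, limited follow-up | 5.12 | 3.29 | 1.56 |
| Mean, also with drop-out | 4.42 | 2.96 | 1.50 |

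Adding the 30-day window (30/30.44 = 0.99 month) to both arms gives 6.11/4.28 = 1.43 and 5.41/3.94 = 1.37. With no PFS effect the ratio is 1.0.

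**Crude percentages under an equal AE hazard.** The AE hazard is not given in the documents, so a range of h from 0.05 to 0.4 per month is assumed, constant and the same in both arms.

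- Without drop-out or limited follow-up, with a window w of 1 month: P = 1 − e^(−hw)·L/(L + h).
- With both, and w = 0.99: P = 1 − e^(−hw)·[1 − h·m(L + h)], where L is PFS hazard plus drop-out hazard: 0.2003 (A) and 0.3260 (B).

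Worked line for h = 0.1 with both. Arm A: m(0.3003) = 3.18, so P = 1 − 0.906 × (1 − 0.318) = 38.2%. Arm B: m(0.4260) = 2.31, so P = 1 − 0.906 × (1 − 0.231) = 30.3%.

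| h per month | Without: A vs B | Excess | With both: A vs B | Excess |
|---|---|---|---|---|
| 0.05 | 27.2% vs 18.9% | 8.3 | 22.5% vs 17.2% | 5.3 |
| 0.1 | 43.9% vs 32.8% | 11.1 | 38.2% vs 30.3% | 7.9 |
| 0.2 | 63.2% vs 51.6% | 11.6 | 58.1% vs 48.9% | 9.2 |
| 0.4 | 80.6% vs 71.9% | 8.7 | 77.3% vs 69.7% | 7.7 |

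The true hazard ratio for AEs is 1.0 in every row.

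**Early AEs.** Counting only events on treatment in the first 28 days (t = 28/30.44 month), P = h/(h + L)·(1 − e^(−(h + L)t)), with L the PFS hazard alone. For h = 0.1 this is 8.2% vs 7.7%, and for h = 0.3 it is 22.5% vs 21.3%: a risk ratio of about 1.05–1.06.

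**Exposure formula.** Take time on SoC as exponential with median 2.4 months (daily hazard 0.2888/30.44 = 0.00949) and doses every d days. Mean covered time is d/(1 − e^(−0.00949d)); the SAP formula gives d − 7 days less.

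| d | Covered (days) | SAP formula (days) | Shortfall |
|---|---|---|---|
| 14 | 112.5 | 105.5 | 7/112.5 = 6% |
| 21 | 116.2 | 102.2 | 14/116.2 = 12% |

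Used as a rate denominator, this would inflate SoC rates by 112.5/105.5 = 1.07 and 116.2/102.2 = 1.14. The SoC mix is not given in the documents, so the two intervals are shown as a range.

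**The case against.** AE evaluation is descriptive, with no test or decision rule. The safety objective is to assess the combinations, whereas the efficacy and QoL objectives are to compare. With 44 vs 22 subjects the false excess is within noise: for 38% vs 30% the standard error is √(0.38×0.62/44 + 0.30×0.70/22) = 12.2 points. Exposure duration and number of cycles are planned variables, and one AE listing shows cycles on treatment, so a reader can see that exposure differs. Rates per patient-month also assume a constant hazard; with early-onset toxicity they dilute the longer-treated arm and can make it look safer.

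Most of this stands as a limit on importance. It does not remove the point: noise does not cancel a systematic shift, and cycle counts are not a common time unit when Arm A cycles last 4 weeks and SoC cycles 3 or 4. The constant-hazard objection is a reason to add a fixed-window percentage beside the rate.

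Three stronger readings are tempting, and the documents do not support them.

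- That the plan expects Arm A to be treated about 1.8 times longer. The documents state no expected treatment duration; 1.77 is the ratio of median PFS under the sizing alternative, before drop-out and limited follow-up.
- That the +7 rule adds to a bias against Arm A. Exposure duration enters no AE table. Its only stated further use is imalumab dose intensity, where 7 days is right. As a denominator it would work against Arm B.
- That the trial would report a false toxicity signal. A shift below one standard error in a descriptive table does not establish that.

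**Conclusion.** The point holds in a limited form. Crude percentages by arm are not like-for-like if the planned PFS effect is real. For AEs that accrue over time the false excess in Arm A is about 5–9 percentage points after drop-out and limited follow-up, or 8–12 without them. It is close to nil for AEs confined to the first 28 days, and absent if PFS does not differ. This rests on exponential PFS, an equal and constant AE hazard of 0.05–0.4 per month, and treatment ending at progression or drop-out.

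The exposure formula is a separate definitional defect. It understates SoC exposure by 7 days for a 2-weekly and 14 days for a 3-weekly drug, and leaves best supportive care undefined. It does not bias the AE tables as planned. Both are worth correcting because the correction is cheap; neither undermines the trial.

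**What to change.** **SAP 8.3.** Keep the crude tables. For Part 2, Arm A vs Arm B, add for all, Grade 3 or higher, serious and related TEAEs:

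- (a) exposure-adjusted incidence to first event per 100 patient-months, with time at risk running from first treatment to the first event or the end of the AE collection window;
- (b) the percentage with an event in a common early window, such as the first 8 weeks.

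**SAP 8.2, before any such rates are computed.** Keep +7 for imalumab. For SoC, define exposure as last minus first dose plus that regimen's own dosing interval. For best supportive care, use C1D1 to the End of Study visit.

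**Cost.** SAP wording and a few extra tables from dates already collected. The patient-month rate assumes a roughly constant hazard, so (a) should not be shown without (b).

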8.4 Clinical Laboratory Evaluations

For hematology, chemistry, and coagulation, the observed values and changes from baseline will be summarized. Change from baseline will be calculated as (value at a treatment cycle – value at baseline). Laboratory results will be classified according to the NCI-CTCAE Version 4.03. Grades are assigned based solely on lab values and CTCAE requirements regarding related clinical signs or symptoms are not required.

Therefore, clinical assessment of the subjects could result in a different grade. Laboratory results not corresponding to CTCAE terms will not be graded. Thresholds are specified in Section 16.2. The number (%) of subjects with values that satisfy CTCAE criteria at any time during treatment will be summarized by test, grade, and visit. Each subject will be categorized based on their post-baseline CTCAE grade at each planned assessment time. Shift tables relative to the CTCAE Grade will be used to summarize the change from baseline to the maximum post-baseline CTCAE grade.

A table will summarize the shift in the absence/presence of protein, glucose, and blood in the urine.

Laboratory results will be summarized in standard international units.

Tables summarizing observed values and changes from baseline and shifts in CTCAE grade will be completed for study cohort. The number (%) of subjects with values that satisfy CTCAE criteria at any time during treatment will be provided for the treatment study cohort and integrated treatment group.

All laboratory test results (including urinalysis) will be presented in by-subject data listings. A list of abnormal laboratory values will also be produced where abnormal is defined as a value with CTCAE Grade 1 or higher. If a subject has at least one abnormal value for a specific analyte, all normal and abnormal values for that subject and analyte will be included in the listing.

Post baseline abnormal hepatic and renal results will be summarized by CTCAE Toxicity Grade among subjects with normal results prior to first dose, and a listing will be created to support this table.

8.4.1 Hematology

Blood samples for hematology will be analyzed for the collected time points. Hematology testing will include complete blood count (CBC) with differential and platelet counts.

8.4.2 Serum Chemistry

Blood samples for serum chemistry will be analyzed for the collected time points. Chemistry tests will include creatinine, creatinine clearance, sodium, potassium, calcium, magnesium, glucose, albumin, alanine aminotransferase (ALT), aspartate aminotransferase (AST), alkaline phosphatase, total bilirubin (TBIL), C-reactive protein (CRP), and blood urea. CTCAE grade for calcium will be based on corrected serum calcium, which will be calculated as follows:

Corrected serum calcium = serum calcium (mg/dL) + 0.8 *[(4 - serum albumin (g/dL)].

8.4.3 Coagulation

Blood samples for coagulation parameters will be collected will be analyzed for the collected time points. The coagulation parameters include international normalized ratio (INR) and activated partial thromboplastin time (aPTT).

8.4.4 Urinalysis

Urine samples will be will be analyzed for the collected time points. A table will summarize the shift in the absence/presence of protein, glucose, and blood in the urine from baseline to day 1 of each cycle and the end of study visit.

8.5 ECG

12-Lead ECGs will be analyzed for the collected time points. ECG conduction times will include PR interval, QRS duration, QT and QTc interval using Fredericia's correction, and the heart rate. The observed values and changes from baseline will be summarized time points collected. Change from baseline will be calculated as (value at a treatment cycle – value at baseline). Frequencies and percentage of values meeting potentially clinically significant (PCS) criteria ([Table 4](#)) at any time will be presented. The denominator for percentages will be the number of patients who have a value at baseline and post-baseline.

Tables summarizing observed values and changes from baseline will be analyzed. The number (%) of subjects with values that satisfy PCS criteria at any time during treatment will be provided.

All summary tables will be provided for the Part 1 and 2 safety analysis set. All ECG data will be included in a listing.

Table 4: Potentially Clinically Significant Post-baseline ECG Conduction Times

Conduction Time	Unit	PCS Criteria
PR Interval	msec	Absolute value \geq 200
QRS Duration	msec	Absolute value \geq 100
QT Interval	msec	Absolute value \geq 450
QTcF Interval	msec	Males: Absolute Value \geq 450 Females: Absolute Value \geq 470

Conduction Time	Unit	PCS Criteria
	msec	Increase from baseline 30 – 60
	msec	Increase from baseline > 60
Heart Rate	beats per minute	Absolute value \leq 40 Absolute value \geq 120

